5.4 STUDY PROCEDURES

The summary of the visits and study procedures to be conducted at scheduled visits is listed in Table 3.

Table 3: Summary of procedures to be conducted at scheduled visits

	V1 Screen & fit	V2 Disp lens#1	at-home ratings (days 1,3, 5) lens#1	V3 1-week progress lens#1	V4 Disp lens#2	at-home ratings (days 1,3, 5) lens#2	V5 1-week progress lens#2	V-Exit
Consent process	x							
CL history and/or lens wear schedule	x	x		x	x		x	
Health & medication	x	x		x	x		x	
Review any problems with eyes/study lenses				x			x	
[REDACTED]								+
[REDACTED]								
[REDACTED]	x							

	V1 Screen & fit	V2 Disp lens#1	at-home ratings (days 1,3, 5) lens#1	V3 1-week progress lens#1	V4 Disp lens#2	at-home ratings (days 1,3, 5) lens#2	V5 1-week progress lens#2	V-Exit
Study lens fitting (both lens types)	x							
Dispense study CLs*		x			x			
[REDACTED]	x	x		x	x		x	
Trial lens fit	x							
[REDACTED]		x		x	x		x	
Study CL fit assessment	x	x		x	x		x	
Complete 'in-office' subjective ratings		x		x	x		x	
[REDACTED]							█	
[REDACTED]			█			█		
[REDACTED]				x			x	
Worn lens collection				x			x	
[REDACTED]	x	x**		x	x**		x	x**
Study completion and Exit								x

* Additional lenses may be dispensed at scheduled or U/S visits if there is lens defect, or lens damage or if there is a valid reason (e.g. lenses dropped or misplaced etc.)

** Not required if visit concurrent with previous one.

¹High Contrast High Illumination

5.5 [REDACTED]

[REDACTED]

[REDACTED]

[REDACTED]

[REDACTED]

[REDACTED]

[REDACTED]

[REDACTED]

[REDACTED]

[REDACTED]

6 MONITORING PROTOCOL ADHERENCE

Adherence to study visit windows, lens wearing schedule, and time windows around other data collection points (i.e. subjective ratings) will be monitored internally by CORE. Deviations from the study plan as described in the protocol will be reported in the study report. As described in Section

15.4, major protocol deviations will be reported to the Sponsor and the University of Waterloo's Office of Research Ethics (ORE) within 7 days of becoming aware of them (as per ORE's guidelines).

7 POTENTIAL RISKS AND BENEFITS TO HUMAN PARTICIPANTS

This is a minimal risk study because of the use of approved products and standard optometric assessments.

Contact lenses in this study will be worn on a daily wear and daily disposable basis. Adverse events and/or complications in the daily wear of soft contact lenses can occur (e.g. inflammation and infection). Complications that may occur during the wearing of contact lenses include discomfort, dryness, aching or itching eyes, excessive tearing, discharge, hyperemia and variable or blurred vision. More serious risks may include photophobia, iritis, corneal edema or eye infection. Although contact lens-related infections are very infrequent, the possibility does exist. The incidence of infection due to daily-wear soft lenses is 0.035%. Almost always an infection will occur only in one eye. Thirty five million Americans who currently wear contact lenses assume this risk.

When contact lenses are worn on a daily wear basis there is a small risk of an adverse event compared to not wearing contact lenses. When contact lenses are worn on an extended wear basis, there is a significantly increased risk of an adverse reaction compared with wearing contact lenses on a daily wear basis.

Additionally, it is possible that participants may experience temporary discomfort associated with the study procedures /products including: burning and stinging, blurred vision, sandiness or grittiness, light sensitivity, dryness, itching, crusty eyes and foreign body sensation.

Participants may not benefit directly from taking part in this study, other than having an opportunity to wear a different contact lens. However, their participation in this study may contribute to scientific research information that may be used in the development of new contact lens products.

Information from this study may help researchers determine new soft contact lens designs to help other people in the future. This study will help the study sponsor to better understand the performance of the products being used in this study.

8 ADVERSE EVENTS

See CORE SOP012_v02 for a description of all adverse events, including management and reporting. An 'adverse event' refers to any undesirable clinical occurrence in a participant, whether

it is considered to be device-related or not. Adverse events (AE) may be classified as ‘unanticipated adverse device effects,’ ‘serious adverse events,’ ‘significant adverse events,’ or ‘non-significant adverse events,’ as defined below, Table 4.

A number of conditions may result in temporary suspension until resolution. These include corneal infiltrates, corneal staining, limbal injection, bulbar injection or tarsal conjunctival abnormalities.

Table 4: Classification of types of adverse event

Classification	Definition
Serious Adverse Event	Those events that are life-threatening, or result in permanent impairment of a body function, or permanent damage to a body structure or necessitate medical (therapeutic) or surgical intervention to preclude permanent impairment of a body function or permanent damage to a body structure.
Significant Adverse Event	Those non-serious adverse events that occur with contact lens usage that are not sight-threatening but are usually symptomatic and may warrant therapeutic management and /or temporary or permanent discontinuation of contact lens wear.
Non-Significant Adverse Events	Those less severe non-serious adverse events that occur with contact lens usage that are not sight-threatening, may or may not be symptomatic and may warrant palliative management, such as ocular lubricants or temporary interruption of contact lens wear.
Unanticipated Adverse Device Effect	Adverse events in a study that were not previously identified in the protocol in terms of nature, severity, or degree of incidence. An Unanticipated Serious Adverse Device Effect is an unanticipated adverse event that is serious in nature and caused by or associated with the device and is considered reportable.

AE classification, coding (for reporting to the sponsor) and reporting details, plus examples, are provided in Table 5.

Table 5: Contact lens adverse event classification, coding and reporting guide

Code	Condition	Reporting
Serious Adverse Events		
01	Presumed infectious keratitis or infectious corneal ulcer	For all serious AEs: Notify sponsor as soon as possible, within 24 hours;
02	Permanent loss of ≥ 2 lines of best spectacle corrected visual acuity (BSCVA)	
03	Corneal injury that results in permanent opacification within central cornea (6mm)	
04	Uveitis or Iritis (e.g. presence of anterior segment inflammation as described in ISO 11980, Annex B)	

05	Endophthalmitis	ORE reporting will be within 24 hours as per requirements
06	Hyphema	
07	Hypopyon	
08	Neovascularization within the central 6mm of cornea	
00	Other serious event	
Significant Adverse Events		
11	Peripheral (outside central 6mm), non-progressive, non-infectious ulcer	Notify sponsor as soon as possible, within 5 working days ; ORE reporting as per requirements
12	Symptomatic corneal infiltrative event	
13	Superior epithelial arcuate lesions (SEALs) involving epithelial split	
14	Corneal staining \geq dense coalescent staining up to 2mm in diameter (e.g. moderate, ISO 11980 grade 3)	
15	Corneal neovascularization \geq 1.0mm vessel penetration (e.g. \geq ISO 111980 Grade 2), if 2 grade change from baseline	
16	Any temporary loss of \geq 2 lines BSCVA for \geq 2wks	
17	Any sign and/or symptom for which participant is administered therapeutic treatment or which necessitates discontinuation of lens wear for \geq 2 weeks	
10	Other significant event	
Non-significant Adverse Events		
21	Conjunctivitis (bacterial, viral or allergic)	Notify sponsor as soon as possible, within 5 working days ; ORE reporting as per requirements
22	Papillary conjunctivitis if \geq mild scattered papillae/follicles approximately 1mm in diameter (e.g. ISO 11890 Grade 2), if 2 grade change from baseline	
23	Asymptomatic corneal infiltrative events	
24	Any sign and/or symptom for which temporary lens discontinuation for $>$ 1 day is recommended (if not already classified)	
20	Other sign and/or symptom warranting classification as a non-significant adverse event	

8.1 NORMAL OR ADAPTIVE SYMPTOMS

Transient symptoms such as end-of-day dryness, lens awareness, itching or burning or other discomfort may occur with contact lens wear and may occasionally reduce wearing time. These are

not reported as adverse events unless in the investigator's opinion they are unexpected in nature, severe or have a high rate of occurrence.

8.2 PROCEDURES FOR ADVERSE EVENTS

Treatment of an adverse event will depend on its nature and severity. Based on the clinical judgment of the investigator the participant may be referred to an ophthalmologist for treatment. The investigator will attempt to determine whether the reaction is related to the test device or a result of other factors. An adverse event form will be completed for each adverse event. If both eyes are involved, a separate adverse event form will be completed *for each eye*. Whenever possible, the adverse event will be photo-documented.

Expenses incurred for medical treatment as part of study participation will be paid by the sponsor (bills and prescription receipts kept). The participant must be followed until resolution or no further change is anticipated and/or referred for further care with the appropriate health care professional and/or recorded as being under appropriate health care as per investigator's discretion. A written report will be completed indicating the subsequent treatment and resolution of the condition.

8.3 REPORTING ADVERSE EVENTS

All potential Serious and Unanticipated Adverse Device Effects that are related or possibly related to participant's participation will be reported to the Principal Investigator and the sponsor within 24 hours of the investigator becoming aware of the event. The Investigator will report the event to the IRB as per IRB requirements (by fax, mail/delivery, phone, or email). All fatal or life threatening events will be reported immediately to the IRB.

Significant and Non-Significant Adverse Events will be reported to the sponsor as soon as possible, but no later than 5 working days after the occurrence. The Investigator will report the event to the ORE as per ORE requirements (by fax, mail/delivery, phone, or email).

[REDACTED]

[REDACTED]

[REDACTED]

[REDACTED]

[REDACTED]

[REDACTED]

[REDACTED]

[REDACTED]

Details of all adverse events will be included in the study report.

9 DISCONTINUATION FROM THE STUDY

Participants discontinued from a study will be reimbursed \$20 per hour for their active involvement in the study (including the initial screening visit). Participants will be discontinued at the discretion of the investigator or sponsor in consideration of participant safety or protocol compliance, or at discretion of the participant. The following is a list of possible reasons for discontinuation from the study:

- Screening failure: Participants will be discontinued if they do not meet the inclusion and exclusion criteria outlined in section 5.1.3.
- Unacceptable performance with products to be used in study: Participants may be discontinued if they are unable to achieve acceptable comfort and /or vision with the study products.
- Positive slit lamp finding: Participants may be permanently discontinued from the study depending on the severity of the condition and on the judgement of the investigator.
- Adverse event: If a participant experiences an adverse event during the study they may be discontinued based on the clinical judgement of the investigator.
- Symptoms: If the participant has persistent symptoms they may be discontinued based on the clinical judgement of the investigator.
- Disinterest, relocation or illness: The participant may choose to discontinue due to reasons within or beyond their control.
- Violation of protocol or non-compliance: The participant will be discontinued if they are unable or unwilling to follow the protocol specified visit schedules and/or study procedures.
- Instillation of topical ocular medication: The participant will be discontinued if they elect to use a topical ocular medication during the study unless that topical ocular medication is prescribed for a limited duration (less than two weeks) to treat a transient condition; in this case the participant may remain an active participant (at the discretion of the investigator) after stopping topical ocular medication following resolution of the ocular condition).
- Lost to follow-up: The participant will be discontinued if they cannot be contacted and do not return for a final exit visit, and if the investigator has made a reasonable effort to contact the participant for a final study visit.
- Premature termination of the study by the sponsor, CORE or the Office of Research Ethics at the University of Waterloo.

A discontinuation form, stating the reason for discontinuation will be completed, which requires the signatures of both the participant and the investigator, except where the participant is lost to follow-up in which case only the signature of the investigator is required.

When a participant chooses to discontinue from the study they will be given the opportunity to withdraw their data from the statistical analysis. This choice will be captured on the discontinuation form.

All discontinuations including their reasons will be included in the final report.

10 DEVICE MALFUNCTIONS

A device malfunction means the failure of the device to meet its performance specification or otherwise perform as intended. Any defective lens that is *likely* to cause or contribute to a *Serious Adverse Event* should be reported to the Principal Investigator and the sponsor **within 24 hours** of the investigator becoming aware of the malfunction. The ORE would also be notified within 24 hours of any device malfunction that may contribute to a *Serious Adverse Event*.

Other defective lenses should be reported to the Sponsor as soon as possible (usually in weekly study updates to the Sponsor).

This clinical study will also ascertain satisfaction or preference with subjective attributes such as comfort, vision, or lens handling. Responses to these subjective questionnaires will not be considered as complaints or device malfunctions.

11 STUDY COMPLETION AND REMUNERATION

At the last scheduled protocol visit a study completion form will be completed, which requires the signatures of both the participant and the investigator. Once their involvement in the study is complete, participants will be informed about receiving feedback following study completion in the Letter of Appreciation. Participant remuneration will be \$20 per scheduled protocol visit hour (including the initial screening visit). Full details are given in the information consent letter.

12 STATISTICAL ANALYSIS AND DATA MANAGEMENT

12.1 STATISTICAL ANALYSIS

Primary comparisons will be between study lenses, however there are some variables collected over time with the same lens and this time comparison will be analysed (e.g. 'at-home ratings on Days 1, 3 and 5).

All data will be analyzed by CORE at the University of Waterloo. Unmasked data analysis will be conducted using Statistica, SPSS, or other appropriate software. Descriptive statistics will be provided on information regarding baseline variables (age, gender, refractive error distribution, etc.). Table 6 lists the main outcome variables and anticipated statistical procedures. All data will be tested for normality of distribution using Shapiro-Wilk tests.

[figure not shown]

Table 6: Statistical analysis to be conducted

Variable	Analysis	Statistical test
Subjective ratings	Descriptive and other statistics	Mean, Median*, Standard Deviation, Minimum, Maximum, Frequency count
	Effect of treatment on outcome variable within subjects (comparison between study days) Effect of time on ratings (comparison over time)	Friedman Wilcoxon matched pairs test
[REDACTED]	Descriptive statistics	Mean, Median*, Standard Deviation, Minimum, Maximum, Count
	Effect of treatment on outcome variable within subjects (comparison between study days)	RMANOVA Paired t-test

* For non-parametric data only

The critical alpha level for statistical significance will be set at 0.05, with no adjustments for multiple comparisons.

All participants who were evaluated will be included in the analysis, unless their removal is agreed by the sponsor due to protocol deviations and/or adverse events. In the event of missing data, individual data points will not be extrapolated from the collected data.

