2 OBJECTIVES

The objective of the study is to evaluate and compare the performance of the study TEST lens to the CONTROL lens, when worn on a daily disposable modality over a period of approximately one week each.

The primary outcome variable of this study is:

- Overall lens fit acceptance at the 1-week follow-up visit.

The secondary outcome variables are:

- Centration (optimal, slight decentration, moderate decentration but not encroaching limbus, excessive & occasionally encroaching limbus), collected at dispense & 1-week visit;
- Post-blink movement in primary gaze, mm, collected at dispense & 1-week visit;
- Push-up tightness in primary gaze (0-100), collected at dispense & 1-week visit.

Participants will be randomized to wear either the test or the control lens first. All lenses will be worn in a daily disposable lens wear modality for one week (-1/+3 days). The study involve up to 5 scheduled visits. The study design is shown in Figure 1.

[figure not shown]

Figure 1: Study Design, visits 1 & 2 may be on a single day, also visits 3 & 4 may be on a single day.

Visit 1: Includes screening, baseline assessments, fitting of both study lenses.

Visit 2: Dispense lens pair #1 (either test or control lens, randomized).

Visit 3: 1-week follow-up assessment of lens pair #1

Visit 4: Dispense of lens pair #2 (either test or control lens)

Visit 5: 1-week follow-up assessment of lens pair #2 and study exit.

- Participants will complete the following in-office subjective ratings on paper using a numeric rating scale (0 – 10) at visits 3 and 5 for each lens type:

- Lens handling;

- [Redacted]
- [Redacted]
- [Redacted]
- [Redacted]

[Redacted]

[Redacted]

[Redacted]

[Redacted]

- [Redacted]
- [Redacted]
- [Redacted]
- [Redacted]

- [REDACTED]
- [REDACTED]
- [REDACTED]
- [REDACTED]
- [REDACTED]

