4.1.3 RANDOMIZATION

A randomization schedule will be generated using a web-based program: (for example www.randomization.com) by CORE's Data management team, and provided to the research assistants for the study. The schedule will determine the order of lens wear for participants in the study. Study investigators will remain masked to the randomization schedule until the study is completed and the database has been locked.

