5 STUDY POPULATION

5.1.1 SAMPLE SIZE CALCULATION

Sample size was calculated using the mean overall fit acceptance from the previous pilot BOXER study [REDACTED]

A sample size of 34 is recommended to detect a mean difference between lens Overall fit acceptance of 0.2 units on the 0 to 4 scale using a standard deviation of 0.4 with 80% power and alpha 0.05 in a two-tailed t-test. Therefore, it is recommended that at least 38 subjects are dispensed in the MIKI study, with a target of 34 to complete.

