5.3 SCHEDULED AND UNSCHEDULED VISITS

This study has 5 visits. The visits are as follows:

- **Visit 1:** Screening, baseline assessments, fitting of both study lenses.
- **Visit 2:** Dispense lens type #1 (normally combined with Visit 1)
- **Visit 3:** 1-week follow-up assessment of lens type #1 (6 to 10 days after Visit 2), worn lens collection
- **Visit 4:** Dispense of lens type #2 (normally combined with Visit 3)
- **Visit 5:** 1-week follow-up assessment of lens type #2 and study exit (6 to 10 days after Visit 4), worn lens collection

A scheduled follow-up visit may only take place when the participant attends wearing the study lenses for 6-8 hours. If this is not the case and the participant is not experiencing any problems with the lenses, the appointment will be rescheduled, ideally within the visit window.

Visits that fall outside of the specified visit windows will be designated as protocol deviations and at the end of the study, the data collected during protocol deviations will be assessed for their suitability to be included in the analysis population.

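### Lens order is randomised over two weeks, but the visible lens comparisons in Table 6 name no period or sequence term; adding one is a cheap precision gain, not the repair of an error

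*Combined protocol and SAP*

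**What the plan says.** Section 2 sets up a two-period crossover: "Participants will be randomized to wear either the test or the control lens first". Section 4.1.3 adds "The schedule will determine the order of lens wear for participants in the study" and does not mention blocking.

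Section 12.1 opens with "Primary comparisons will be between study lenses". Table 6 describes the lens comparison as "Effect of treatment on outcome variable within subjects (comparison between study days" and lists Friedman and Wilcoxon matched pairs for subjective ratings, and RMANOVA and paired t for a row whose label is redacted. The only time effect that section 12.1 describes is within one lens (the at-home ratings on Days 1, 3 and 5), which is not a crossover period effect. Section 12.1 also says "All data will be tested for normality of distribution using Shapiro-Wilk tests", so an outcome might move to the nonparametric route.

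Section 5.1.1 sizes the trial to "detect a mean difference between lens Overall fit acceptance of 0.2 units on the 0 to 4 scale". Its other inputs are an SD of 0.4, a two-sided t-test at the 5% level and power of 80%. The result is 34 completers from 38 dispensed.

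**The concern.** In a two-period crossover, each person's lens difference is also a week 1 versus week 2 difference. If grades drift between the weeks, for whatever reason, that drift adds to the difference in one order and subtracts from it in the other. A plain paired test treats the drift as noise. If the two orders are not equally filled, part of the drift also lands in that trial's lens estimate.

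Paired t, matched-pairs and Friedman tests have no place for a period term. RMANOVA could carry order, but the plan does not say that it will. At stake is some power in a trial with little to spare (33 completers would already fall below 80%), and some protection against an uneven split.

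**Working it through.** **Inputs.** From section 5.1.1: difference 0.2, SD 0.4, two-sided alpha 0.05, 34 completers. Assumed: 0.4 is the SD of within-person differences and is free of period variation; differences are normal; the shift (week 2 minus week 1) is 0, 0.1, 0.2 or 0.3. The documents give no period effect.

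**1. The plan's own figure.** Paired t-test, noncentrality 0.2 × √34 / 0.4 = 2.92 on 33 df: power 80.8%. With n = 33 it is 79.5%. So 34 is reproduced, as a paired calculation.

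**2. Model.** Test minus control has mean 0.2 − shift if test is worn first and 0.2 + shift if control is first, with residual SD 0.4.
- Paired test: overall mean of the differences, 33 df.
- Period-adjusted test: average of the two order-specific means, standard error (s/2) × √(1/n1 + 1/n2), 32 df.

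**3. Validity.** Averaged over simple randomisation, the paired test has zero bias and type I error of about 5% at every shift tried. At 17/17 its type I error is at or below 5% (4.3% at a shift of 0.1, 2.9% at 0.2).

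**4. Cost of the term with no shift.**
- 17/17: 80.8% falls to 80.7%, a cost of 0.1 point.
- Averaged over random splits: about 1.3 points.
- 21/13: standard error 0.2 × √(1/21 + 1/13) = 0.0706, noncentrality 0.2 / 0.0706 = 2.83 on 32 df, power 78.5%. The cost is 2.3 points (2.4 by simulation).

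**5. Power by shift (simulation).**

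| Shift | Random split: paired | Random split: adjusted | 17/17: paired | 17/17: adjusted |
|---|---|---|---|---|
| 0 | 81% | 79–80% | 81% | 81% |
| 0.1 | 78% | 79–80% | 79% | 81% |
| 0.2 | 71–72% | 79–80% | 73–74% | 81% |
| 0.3 | 62% | 79–80% | 64% | 81% |

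Over random splits the term breaks even at a shift of about 0.07 to 0.08. It gains about 1 point at 0.1 and about 8 at 0.2. At 17/17 it gains about 2 and 7 points.

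**6. The same loss as sample size.** Under random splits the paired test faces an SD of √(0.16 + shift²) = 0.412, 0.447 and 0.500, and needs about 36, 42 and 52 completers for 80% power. At an even split the shift inflates only the estimated error, not the true variance of the mean. About 40 completers then suffice at a shift of 0.2, and 46 at 0.3.

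**7. Uneven orders.** The estimate moves by shift × (n1 − n2)/34. At 21/13 and a shift of 0.2 this is 0.2 × 8/34 = 0.047, and paired type I error is about 7%. A split this uneven or worse has probability 0.23 under simple randomisation. At 20/14 the move is 0.2 × 6/34 = 0.035 and type I error stays at about 5%.

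**8. If 0.4 already contains period variation.** Paired power is then about 81% over random splits at shifts of 0.1 to 0.3, and 81%, 84% and 90% at 17/17: no shortfall against plan. The residual SD is √(0.16 − shift²), which is 0.387 at 0.1 and 0.346 at 0.2. The adjusted test at 17/17 then has noncentrality 0.2 × √34 divided by that SD, which is 3.01 and 3.37, and power of about 83% and 90%, against 81% and 84% for the paired test.

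**The case against.** The strongest reply is that nothing here is wrong. A paired t-test matches the sample size calculation, is unbiased over the randomisation and holds its type I error. That stands, and it fixes the grade of the point. A reader might infer that leaving out the period term biases the lens comparison or invalidates the test; step 3 shows that it does not.

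Second, the gain rests on a shift that no document reports. That also stands. Material gains need a shift near the 0.2 that the trial targets, and the design leans against one: participants are habitual soft-lens wearers, both lenses are tried at Visit 1, and section 5.3 says "A scheduled follow-up visit may only take place when the participant attends wearing the study lenses for 6-8 hours". A reader might take the fixed wear time as a sign that a large shift is possible. It points the other way, since equal wear before both gradings makes a shift less likely.

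Third, redaction limits the reading. The RMANOVA/paired t row has no visible label, so the primary outcome's test is inferred from the t-test in section 5.1.1. Sections 3 to 4.1.2 are not visible, so blocking may be specified there. About 77% of simple-random splits are 20/14 or more even, so 21/13 is not the typical case.

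What survives is narrow. No visible text uses the order that the trial randomises, and using it costs almost nothing.

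**Conclusion.** Minor, and worth adopting as a cheap improvement; confidence is medium. On the assumptions listed, the term costs 0.1 to about 2.4 power points if there is no shift, depending on the split. It repays that once the shift passes about 0.07 to 0.08 under random splits, and is worth 7 to 8 points if the shift reaches 0.2. It also removes the movement in the lens estimate when the orders are uneven.

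The documents do not support a claim that the trial is underpowered or needs more than 34 completers. The larger sample sizes in step 6 apply only to a plain paired test, an assumed shift and an SD that excludes period variation. If the pilot SD already contains that variation, the planned power is kept without the term, and the term adds to it once the shift is past the break-even point.

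**What to change.** In section 12.1 and Table 6, state that overall fit acceptance at 1 week will be compared between lenses with a linear mixed model: lens, period and sequence as fixed effects, participant as random effect, and the lens difference reported with its 95% CI. For complete pairs this equals the two-sequence t-test on within-person differences.

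If a nonparametric test is used for this outcome, the matching choice is the rank-sum test on within-person week 1 minus week 2 differences, compared between the two orders. With no shift it costs about 1 to 2 power points against the matched-pairs test. That figure comes from simulations whose grade step (0.25), mean (3.2) and SDs (0.3 between persons, 0.28 per visit) are all assumed.

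Leave the Day 1, 3 and 5 comparisons within a lens as planned. The change needs no new data, visits or participants, and the target stays at 34. Its price is SAP wording, one degree of freedom and the small power costs given in step 4 of the working.
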